9.8 Permitted Concomitant Medications

All concomitant medications taken during the study will be recorded in the eCRF with indication, dose information, and dates of administration. Any medication that is not specifically prohibited is allowed.

Throat or cough lozenges (also known as a candies, drops, sweets or pastilles) and mucolytic agents are permitted.

9.9 **Prohibited Concomitant Medications**

A list of prohibited concomitant medications is provided in Appendix 1.

Due to their potential effect on cough reflex sensitivity, the use of opioids, dextromethorphan, gabapentin, pregabalin, baclofen, antihistamines, thalidomide, benzonatate or tricyclic antidepressants (e.g. amitriptyline) for treatment of cough is not allowed throughout the study (through to Visit 8). Subjects must have discontinued these drugs at least 4 weeks prior to the Baseline visit and should not have them started during the study. Subjects may, however, be permitted to continue to use these drugs if they have been prescribed solely for the management of another disorder (eg neuropathic pain, depression) and the dose has been stable for at least 1 month prior to screening.

Protocol No.: ORV-PF-01 Final V4.0 (US) Page 41 of 85

Angiotensin converting enzyme (ACE) inhibitors are not allowed within 3 months of Screening and throughout the study.

The use of other NK_1 antagonists (e.g., aprepitant, fosaprepitant, rolapitant) is not permitted for any reason from 4 weeks before the Baseline visit until completion of Visit 8

Strong or moderate inhibitors of CYP3A4 are excluded from the day of Visit 2 until one week after the last dose of IMP in the study.

The following classes of medication are excluded from Screening until one week after the last dose of IMP in the study:

- Strong or moderate inducers of CYP3A4 (including but not limited to rifampicin, carbamazepine, efavirenz, bosentan, modafinil, St. John's Wort)
- Strong or moderate inhibitors of P-glycoprotein inhibitors

9.10 Other Study Restrictions

9.10.1 Driving and Operation of Machinery

Somnolence and dizziness have been identified as non-serious adverse reactions to orvepitant. Subjects will be instructed neither to drive nor operate machinery if they experience somnolence or dizziness.

9.10.2 Contraception

Female subjects of childbearing potential are excluded from the study and hence there are no contraceptive requirements for them.

Male subjects who are sexually active with a female partner of child-bearing potential (i.e., the partner is not surgically sterilised or postmenopausal) must agree to use a condom for the duration of participation in the study and for 30 days after the last dose of study medication.

Protocol No.: ORV-PF-01 Final V4.0 (US) Page 42 of 85

CONFIDENTIAL ORVEPITANT

Product:

Protocol No.: ORV-PF-01 NeRRe Therapeutics Ltd

STUDY SCHEDULE 10.

Table 2: Schedule of Events

	Screening	Baseline	Treatment Period A	t Period A	End of Wash-	Treatmen	Treatment Period B	Follow-up/
	A ISIL		Week 2f	Week 4	Period B	Week 2 ^f	Week 4	Termination ^b
Visit (V) Number	1	2	3	4	5	9	7	œ
Timing of visit	Within 14 to 28 days of V2	Day 0	14 days after V2	28 days after V2	21 days after V4	14 days after V5	28 days after V5	14 days after V7
Allowable window	N/A	0	±3 days					
Informed Consent ^a	X							
Medical History & demographics	X							
Physical examination	X	X°						Χc
Pulmonary function tests (spirometry)	χi	X		X	X		X	X
Inclusion/exclusion criteria	X	$^{ m pX}$						
Concomitant medication review	X							XX
Vital signs ^e	X	X		X	X		X	X
12-lead ECG	X	X		X	X		X	X
AE recording		X						XX
Issue eDiary/Training/Compliance check	X	X	X	X	X	X		
Randomisation		X						
eDiary completion (once daily) ⁱ	X						X	
Study drug dispensing/training		X			X			
Study drug collection/compliance check				X			X	
Ambulatory cough monitoring		X		X			X	
Daily dosing (evening before bed)			X _h	X		X	X	
Leicester Cough Questionnaire		X		X	X		X	
Hull Airway Reflux Questionnaire		X		X			X	
K-BILD Questionnaire		X		X	X		X	
PROMIS SF SD 8b		X		X	X		X	
Hospital Anxiety and Depression Scale		X		X	X		X	
Global ratings of status/change in cough		Xg	X	X	X	X	X	X
Biomarker samples		X		X	X		X	
Clinical chemistry and haematology	X	X		X	X		X	X
Blood sample for orvepitant concentration				X	X		X	
Urinalysis	X	×		×	×		×	X

Page 43 of 85 Final V4.0 (US) Protocol No.: ORV-PF-01 16-MAY-2024

CONFIDENTIAL

Product: ORVEPITANT

Protocol No.: ORV-PF-01 NeRRe Therapeutics Ltd

rs	Informed consent will be obtained prior to any screening procedures being performed. Consent can be obtained prior to the Screening Visit or at the actual visit.
م	An Early Withdrawal/Safety Follow-up visit will be performed if the subject withdraws after the Baseline visit. This visit will consist of the same assessments as the Follow-up visit and should be scheduled within 14 days of the early termination date or discontinuation of investigational product.
o	Symptom directed examination, if required.
P	Any changes that may impact eligibility are reviewed
9	Systolic and diastolic blood pressure, pulse rate, temperature, arterial oxygen saturation (measured using a pulse oximeter). In addition, weight is recorded at visits 2 and 8.
ţ.	These visits will be conducted remotely/virtually (by phone or videoconference)
50	At Baseline only the global rating of status is recorded
۹	Starting the evening of the day following the Baseline and End of Wash-out Visits (to allow for completion of ambulatory cough monitoring at Baseline). Finishing the evening of the Week 4 visit.
	Used to record IPF Coughing Severity Scale, additional cough scales and other symptom scale scores. Last day of completion is the evening of Visit 7.
·r	At screening, DLCO also measured if required

10.1 Efficacy Assessments

10.1.1 IPF Coughing Severity Scale

The IPF Coughing Severity Scale is a numerical rating scale (NRS) which will be completed in the eDiary during the study, starting at Visit 1 and continuing through to the day of Visit 7. It will be completed once a day by the subject, in the evening, just before retiring to bed.

Subjects are asked to rate the severity of their coughing in the past 24 hours using an 11-point scale ranging from 0 (no coughing) to 10 (coughing as bad as you can imagine) (Appendix 2).

The eDiary will have a reminder function and will include a time window during which completion is permitted. On expiry of the window the assessment will be locked and if it hasn't been completed will be considered missing for that day.

Daily scores will be transferred from the eDiary provider's database to statistical analysis. Scores will be averaged over 7-day periods to provide weekly average IPF Coughing Severity Scale scores for each assessment timepoint. A minimum of 4 daily assessments will be required for a valid weekly average.

10.1.2 Additional Cough Scales

10.1.2.1 Early morning cough scale

The early morning cough scale will be completed in the eDiary during the study in the same manner as the IPF Coughing Severity Scale.

Subjects are asked to rate the severity of their coughing first thing that morning on waking or rising using an 11-point NRS ranging from 0 (no coughing) to 10 (coughing as bad as you can imagine) (Appendix 2).

10.1.2.2 Rest of the day cough scale

The rest of the day cough scale will be completed in the eDiary in the same manner as the IPF Coughing Severity Scale.

Subjects are asked to rate the severity of their coughing during the rest of the last 24 hours (excluding the coughing first thing on waking) using an 11-point NRS ranging from 0 (no coughing) to 10 (coughing as bad as you can imagine) (Appendix 2).

10.1.3 Other Symptom Scales

10.1.3.1 Urge to Cough Scale

The urge to cough scale will be completed in the eDiary during the study in the same manner as the IPF Coughing Severity Scale.

Subjects are asked to rate the severity of their urge to cough in the past 24 hours using an 11-point NRS ranging from 0 (no urge to cough) to 10 (urge to cough as bad as you can imagine) (Appendix 2).

10.1.3.2 Cough Frequency Scale

The cough frequency scale will be completed in the eDiary during the study in a similar manner to the IPF Coughing Severity Scale.

Subjects are asked to rate the frequency of their coughing in the past 24 hours using a 5-point verbal rating scale ranging from Never to All the time (Appendix 2).

Protocol No.: ORV-PF-01 Final V4.0 (US) Page 45 of 85

10.1.3.3 Dyspnoea Scale

The dyspnoea scale will be completed in the eDiary during the study in the same manner as the IPF Coughing Severity Scale.

Subjects are asked to rate the severity of their shortness of breath in the past 24 hours using an 11-point scale ranging from 0 (no shortness of breath) to 10 (shortness of breath as bad as you can imagine) (Appendix 2).

10.1.4 Global Rating of Status Questionnaire for Cough Severity

The global rating of status questionnaire comprises three questions that subjects will complete at Visits 2, 3, 4, 5, 6, 7 and 8

Subjects will be asked to rate the overall severity of:

- All coughing
- Coughing first thing in the morning
- Any other coughing

over the past week as either none, mild, moderate, severe or very severe (Appendix 3).

It will be completed during the study visit by the subject directly onto a tablet device except at visits conducted remotely in which the subjects' verbal rating will be transcribed onto the tablet by a member of the site staff.

10.1.5 Global Rating of Change Questionnaire for Cough Severity

The global rating of change questionnaire comprises three questions that subjects will complete at Visits 3, 4, 5, 6, 7 and 8

Subjects will be asked to rate the overall change in severity since starting the study of:

- All coughing
- Coughing first thing in the morning
- Any other coughing

They will select one of 7 responses that range from very much worse through no change to very much better (Appendix 3).

It will be completed during the study visit by the subject directly onto a tablet device except at visits conducted remotely in which the subjects' verbal rating will be transcribed onto the tablet by a member of the site staff.

10.1.6 Ambulatory Cough Monitor

Subjects will be fitted with an ACM (the Leicester Cough Monitor¹⁰ [LCM]) to record cough frequency over 24 hours at Visits 2, 4 and 7.

The LCM will be started prior to the subject leaving the clinic to monitor cough frequency over 24 hours. After this period, the subjects will either return the monitor to the clinic or collection from the subjects will be organised. Cough frequency will be determined by a central evaluation service

Protocol No.: ORV-PF-01 Final V4.0 (US) Page 46 of 85

¹⁰ Intellectual property rights to the Leicester Cough Monitor owned by [name] and King's College Hospital NHS Foundation Trust

Product: ORVEPITANT Protocol No.: ORV-PF-01 NeRRe Therapeutics Ltd

(Department of Respiratory Medicine, Kings College Hospital, London, UK [Kings]) using standardised methodology and with appropriate quality control processes.

On the three occasions that cough frequency is assessed, patients will be provided with a paper form on which they will record the times during the recording period that they were asleep.

Analysed data will be transferred to for statistical analysis. Kings will be provided with subject identifier information but will not have access to the randomisation code.

10.1.7 Leicester Cough Questionnaire

The LCQ is a 19-item questionnaire that assesses cough-related Quality-of-Life. It has three domains (physical, psychological and social). The total score range is 3-21 and domain scores each range from 1-7; a higher score indicates a better Quality-of-Life (Appendix 4).

Subjects will complete the LCQ during Visits 2, 4, 5 and 7.

It will be completed during the study visit by the subject directly onto a tablet device.

10.1.8 Kings Brief Interstitial Lung Disease (K-BILD) Health Status Questionnaire

The K-BILD is a brief, validated, self-completed health status measure for interstitial lung diseases. It comprises 15 questions in three domains (psychological, breathlessness and chest symptoms, Appendix 5). The recall period is 2 weeks. It will be completed by the subject at Visits 2, 4, 5 and 7

It will be completed during the study visit by the subject directly onto a tablet device.

10.1.9 **PROMIS SD SF 8b**

The PROMIS (Patient-Reported Outcomes Measurement Information System, part of the National Institutes of Health Roadmap initiative designed to improve PROs using state-of-the-art psychometric methods) SD SF 8b is a short form questionnaire to assess sleep disturbance (Appendix 6). It comprises eight questions and will be completed by subjects at Visits 2, 4, 5 and 7.

It will be completed during the study visit by the subject directly onto a tablet device.

10.1.10 Hospital Anxiety and Depression Scale

The HADS is a widely used tool for assessing anxiety and depression in a general population. It comprises 14 questions, seven each for anxiety and depression, (Appendix 7) and will be completed by subjects at Visits 2, 4, 5 and 7.

It will be completed during the study visit by the subject directly onto a tablet device.

10.1.11 Hull Airway Reflux Questionnaire

The Hull Airway Reflux Questionnaire is a 14-item questionnaire that assesses airway hypersensitivity, particularly that associated with reflux of gastric contents (Appendix 8). It will be completed at Visits 2, 4 and 7.

It will be completed during the study visit by the subject directly onto a tablet device.

Protocol No.: ORV-PF-01 Final V4.0 (US) Page 47 of 85

10.2 Safety Assessments

10.2.1 Medical history and concomitant diseases

A review of medical and medication history will be performed at Screening to confirm subject eligibility. This must be reviewed and by the investigator or a medically qualified sub-investigator. All medically relevant information should be recorded, regardless of the time since the date of diagnosis.

History should include (but not be limited to):

- All medications currently being taken, and any other medications taken within six months before the Screening Visit
- The date of diagnosis of IPF, which should be consistent with the requirements of the 2018 or 2022 joint ATS/ERS/JRS/ALAT Clinical Practice Guideline, and the date of onset of the subject's chronic cough
- Any other respiratory disorders
- Relevant medical history relating to cardiac, vascular, neurological, gastrointestinal, renal, hepatic, psychiatric disorders, and any other diseases.

10.2.2 Physical examinations

A full physical examination will be conducted at the Screening visit and a symptom directed physical examination at other visits, as shown in the Schedules of Events (Table 2). This will be completed by a physician or an appropriately qualified delegate.

A full physical examination is composed of a review of the following body systems:

- General appearance
- Skin
- Head, eyes, ears, nose and throat
- Respiratory
- Cardiovascular
- Abdomen (including liver and kidneys)
- Musculoskeletal
- Neurological

Any abnormalities that are identified at the Screening Visit will be documented on the medical history eCRF page. Any changes (including new and worsening findings) between the Screening Visit and final study visit should be documented in the subject's source notes and recorded as AEs on the AE eCRF page.

If an improvement/resolution of a physical examination finding documented in the subject's medical history occurs during the study, it should be recorded in the subject's source notes. If there is resolution of a physical examination finding previously noted as an AE, then the event resolution and stop date should be recorded on the AE eCRF page and documented in the subject's notes.

Protocol No.: ORV-PF-01 Final V4.0 (US) Page 48 of 85

10.2.3 **Pulmonary function**

Lung function will be assessed by spirometry in accordance with the joint 2019 American Thoracic Society and European Respiratory Society Technical Update on Standardization of Spirometry. ¹¹ Measurements will be made and assessed locally at the study sites. The same model of spirometer should be used throughout the study for any given subject.

Spirometry will be performed at Visits 1, 2, 4, 5, 7 and 8.

Where possible (recognising that patients with IPF often find spirometry challenging), the highest values from three technically satisfactory attempts will be recorded and used for the purpose of eligibility. If three technically satisfactory attempts cannot be completed by the subject, the best attempt should be used.

Short acting bronchodilator agents should be withheld for at least 12 hours before a spirometry assessment and long acting bronchodilator agents should be withheld for at least 24 hours.

10.2.4 12-Lead ECGs

Resting 12-lead ECG data will be recorded after the patient has rested for at least five minutes in a semi-recumbent position. The same model of ECG recorder should be used throughout the study for any given subject.

ECGs will be recorded Visits 1, 2, 4, 5, 7 and 8

ECG reports must be reviewed, signed, and dated by the Investigator or delegated physician. Reports will then be filed with the subject's medical record. The Investigator will comment on all abnormal findings and determine whether they are clinically significant. These assessments will be recorded in the eCRF, and clinically significant findings must also be reported as AEs in the eCRF.

10.2.5 Clinical chemistry

Blood for clinical chemistry assessments will be collected and sent to the central laboratory for analysis at Visits 1, 2, 4, 5, 7 and 8

The following clinical chemistry parameters will be assessed: sodium, potassium, glucose, urea/urea nitrogen, creatinine, creatine kinase, albumin, calcium, phosphate, bilirubin (total), alkaline phosphatase, aspartate transaminase, alanine transaminase, gamma glutamyl transferase, bicarbonate, magnesium, chloride, total protein. Subjects do not need to fast before clinical chemistry samples are taken.

Clinical chemistry test reports must be reviewed, signed, and dated by the Investigator or delegated physician. Reports will then be filed with the subject's medical record. The Investigator will comment on all abnormal results and determine whether they are clinically significant. Clinically significant findings must also be reported as adverse events in the eCRF.

10.2.6 Haematology

Blood for haematology assessments will be collected and sent to the central laboratory for analysis at Visits 1, 2, 4, 5, 7 and 8.

Protocol No.: ORV-PF-01 Final V4.0 (US) Page 49 of 85

¹¹ Graham B, Steenbruggen I, Miller M, Barjaktarevic I, Cooper B, Hall G, et al. Standardization of Spirometry 2019 Update. An Official American Thoracic Society and European Respiratory Society Technical Statement. Am J Respir Crit Care Med 2019;200,e70–e88.

The following haematology parameters will be assessed: red blood cell count, white blood cell count, haematocrit, haemoglobin, mean cell volume, platelet count and white cell differentials.

All haematology test reports must be reviewed, signed, and dated by the Investigator or delegated physician. Reports will then be filed with the subject's medical record. The Investigator will comment on all abnormal results and determine whether they are clinically significant. Clinically significant findings must also be reported as adverse events in the eCRF.

10.2.7 Urinalysis

Urine for urinalysis assessments will be collected and sent to the central laboratory for analysis at Visits 1, 2, 4, 5, 7 and 8.

Parameters to be measured will comprise glucose, bilirubin, ketones, specific gravity, blood, pH, protein, urobilinogen, nitrites, leucocyte esterase, sedimentation.

Urinalysis test reports must be reviewed, signed, and dated by the Investigator or delegated physician. Reports will then be filed with the subject's medical record. The Investigator will comment on all abnormal results and determine whether they are clinically significant. Clinically significant findings must also be reported as adverse events in the eCRF.

10.2.8 Vital signs

Vital signs (systolic and diastolic blood pressure, pulse rate, temperature, arterial oxygen saturation [SpO2]) will be measured at Visits 1, 2, 4, 5, 7 and 8.

Blood pressure will be measured using a standardised process:

- Subject should sit for ≥5 minutes with feet flat on the floor and measurement arm supported so that the midpoint of the manometer cuff is at heart level
- Use an automatic blood pressure device with an appropriately sized cuff with the bladder centered over the brachial artery
- Measure and record the blood pressure using the same arm throughout the study

SpO2 will be measured using a pulse oximeter.

Additionally, weight will be measured at Visits 2 and 8.

All measurements are to be recorded on the Vital Signs eCRF.

All vital signs must be reviewed by the Investigator or delegated physician. The Investigator will comment on all abnormal results and determine whether they are clinically significant. These assessments will be recorded in the eCRF, and clinically significant findings must also be reported as adverse events in the eCRF.

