8.3 Safety endpoints

The safety endpoints comprise the following:

Assessments	Safety endpoints	
Pulmonary function tests measured using a spirometer	Change from Baseline to each post-baseline assessment time-point in forced vital capacity (FVC), forced expired volume in one second (FEV1), peak expiratory flow rate and vital capacity (VC)	
Adverse events recorded throughout the study	 Number of treatment emergent adverse events Number of treatment emergent serious adverse events Number of treatment emergent adverse events resulting in treatment discontinuation Severity of treatment emergent adverse events Number of treatment emergent related adverse events 	
Physical Examination	Treatment emergent changes in physical examination will be recorded as adverse events	
Vital Signs (pulse rate, systolic and diastolic blood pressure, arterial oxygen saturation, temperature, weight).	Mean change from Baseline to each post-baseline assessment time-point in each vital sign: Systolic blood pressure Diastolic blood pressure Pulse rate Temperature Arterial oxygen saturation Weight Clinically significant changes in vital signs are recorded as adverse events	

Protocol No.: ORV-PF-01

Product: CONFIDENTIAL ORVEPITANT

Haematology, clinical chemistry Mean change from Baseline to each post-baseline and urinalysis parameters assessment time-point in each haematology parameter Mean change from Baseline to each post-baseline assessment time-point in each clinical chemistry parameter Shift from Baseline to each post-baseline assessment time-point in each urinalysis parameter Clinically significant changes in laboratory parameters are recorded as adverse events 12-lead ECG parameters Proportion of subjects with clinically significant abnormal ECG findings at each post-baseline assessment time-point Proportion of subjects with non-significant abnormal findings at each post-baseline assessment time-point Change from Baseline to each post-baseline assessment time-point in ECG intervals: PR QT, QTc and QTcF RR **ORS** Proportion of subjects at each post-baseline assessment time-point with maximum absolute QTcF values by category ≤450, >450 to ≤480, >480 to ≤500, >500 msec Proportion of subjects at each post-baseline assessment time-point with maximum change from baseline in QTcF values by category \leq 0, >0 to \leq 30, >30 to \leq 60, >60 msec Clinically significant changes in ECG findings are recorded as adverse events

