11.1 General Statistical Considerations

Subjects will be randomised to cohort and then further randomised to treatment order.

The primary objective of the study is to evaluate the effect of orvepitant once daily on cough severity, as perceived by patients, with IPF. The corresponding primary endpoint is the mean change from Baseline to Week 4 (the last 7 days of treatment) in weekly average of the daily IPF Coughing Severity Scale score.

The primary objective will be assessed by testing the following hypotheses for each orvepitant dose group separately:

Null hypothesis (H0): There is no difference in the mean change in mean IPF Coughing Severity Scale scores for the orvepitant treatment group compared to placebo.

H0: μ (active) = μ (placebo)

Alternative hypothesis (H1): There is a difference in the mean change in mean IPF Coughing Severity Scale scores for the orvepitant treatment group compared to placebo.

H1: μ (active) $\neq \mu$ (placebo)

Each comparison will be carried out at the two-sided 5% level of statistical significance. No adjustment will be made for the multiple orvepitant versus placebo group comparisons in this phase 2 study (two in total: 10 mg versus placebo, 30 mg versus placebo) as each dose cohort is tested independent (versus the corresponding placebo) and each is adequately powered.

11.1.1 Definition of Baseline

Baseline values will be defined separately for each treatment period, unless stated otherwise.

For the primary efficacy endpoint, period-specific baseline will be used in the analysis, which is the average of the 7 calendar days up to and including the date of Visit 2 for Treatment Period A and the average of 7 calendar days up to and including the date Visit 5 for Treatment Period B.

For secondary efficacy endpoints related to change from baseline, the period-specific baseline will be used when available; for those endpoints for which a period-specific baseline is not available (cough frequency and Hull Airway Reflux Questionnaire), the baseline in Treatment Period A will be used.

For safety assessments, baseline will be Visit 2 for Treatment Period A and for Treatment Period B it will be Visit 5.

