11.9 Statistical Methods for Safety Parameters

Safety data will be summarised descriptively for each treatment. No formal inferential tests will be performed on safety data.

The number of treatment emergent AEs (TEAEs), and subjects with TEAEs, will be compared between treatments. TEAEs are defined as AEs that first occurred or worsened in severity after the first dose of IMP.

TEAEs will be summarised for all causality AEs and for treatment-related AEs (those with related relationship to IMP and missing). TEAEs will be summarised by MeDRA body system and preferred term. TEAEs will also be reported by severity.

Any deaths, SAEs and AEs leading to discontinuation of IMP administration will also be summarised by treatment group.

SAEs will be presented in a similar way to AEs.

Vital signs will be summarised for each treatment group by visit. Summary statistics will be presented for absolute values and the change from Baseline.

ECGs will be assessed by the Investigator for abnormal findings. These will be categorised and summarised as normal, abnormal-not clinically significant, or abnormal-clinically significant. ECG intervals will be recorded and summarised as absolute values and changes from Baseline.

Clinical laboratory data for individual subjects will be listed and any out of range values will be highlighted. Laboratory data will be summarised for each treatment group by visit. Summary statistics will be presented for absolute values and change from Baseline, as well as an analysis of shifts from Baseline.

Extent of exposure and compliance will be summarised.

Selected safety parameters will be summarised for the following sub-groups:

- By use of concomitant disease modifying therapies at Baseline (yes, no [nintedanib or pirfenidone])

Protocol No.: ORV-PF-01 Final V4.0 (US) Page 58 of 85

CONFIDENTIAL Protocol No.: ORV-PF-01
NeRRe Therapeutics Ltd

Product: ORVEPITANT

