### 8 SAFETY ANALYSES

Safety data will be summarised descriptively for each treatment. That is, safety data will be summarised for two doses of orvepitant (10 mg and 30 mg separately), and two placebo groups separately by cohort.

No formal inferential tests will be performed on safety data.

Safety analysis will be carried out using the SS population.

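### Weight is a safety endpoint measured only at Visits 2 and 8, so a completer's change spans both treatments and cannot isolate an orvepitant effect

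*Protocol*

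**What the plan says.** **Endpoint.** Protocol 8.3 puts weight in the vital-signs row, with the endpoint "Mean change from Baseline to each post-baseline assessment time-point in each vital sign". The synopsis and SAP 3.4 also list weight there.

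**Measurement.** Protocol 10.2.8 says "Additionally, weight will be measured at Visits 2 and 8", and the footnote to the Schedule of Events (Protocol Table 2) agrees: "In addition, weight is recorded at visits 2 and 8". The synopsis gives the same two occasions. For the other vital signs, Protocol 10.2.8 reads "temperature, arterial oxygen saturation [SpO2]) will be measured at Visits 1, 2, 4, 5, 7 and 8", so those are taken at both ends of each treatment period.

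**Presentation.** Protocol 11.9 states "Vital signs will be summarised for each treatment group by visit", and SAP 8 states "Safety data will be summarised descriptively for each treatment".

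**Baseline.** Protocol 11.1.1 reads "For safety assessments, baseline will be Visit 2 for Treatment Period A and for Treatment Period B it will be Visit 5", and SAP 5.2.2 matches it. Both add that if the Period B baseline is missing, the Visit 2 value is used first.

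**Vital-signs analysis in the SAP.** SAP 8.3 names blood pressure, pulse rate, temperature and oxygen saturation. It does not name weight. Apart from the endpoint list, the SAP mentions weight only as a demographic variable (SAP 6.2).

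**The concern.** These provisions cannot all be met for weight. A completer has no weight at Visit 4, so Period A has no post-baseline value. There is none at Visit 5, so Period B has no baseline of its own, and none at Visit 7, so Period B has no end-of-treatment value. The one change that can be computed runs from before the first dose of the study to two weeks after the last treatment period, and it includes both treatments.

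Safety is one of the two primary objectives. Protocol 8.6.1 justifies the design partly by the ability to compare safety findings with a placebo period. For weight, completers supply no orvepitant-versus-placebo pair. If a by-treatment weight table were produced anyway, its columns would carry treatment labels that do not describe what the subjects received over the interval.

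**Working it through.** **1. Timeline.** Protocol 9.5 states up to 17 weeks of participation. Screening 4 + Period A 4 + wash-out 3 + Period B 4 + follow-up 2 = 17 weeks, so the stated figure reproduces. From Table 2, Visit 2 to Visit 8 is 28 + 21 + 28 + 14 = 91 days (nominal; each visit has a window of ±3 days).

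**2. What the change contains.** In both sequences the 91 days include one 28-day orvepitant course and one 28-day placebo course. The sequences differ only in the time from the end of the orvepitant course to Visit 8:
- orvepitant then placebo: 21 + 28 + 14 = 63 days
- placebo then orvepitant: 14 days

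**3. Contrast if the change were labelled by Period B treatment.** The documents do not state this labelling; it is examined as one way the table could be built. Let E be the weight effect at the end of an orvepitant course, and let f(t) be the fraction left t days after the course ends. The orvepitant column (placebo-then-orvepitant subjects) shows f(14)·E. The placebo column (orvepitant-then-placebo subjects) shows f(63)·E. The difference is [f(14) − f(63)]·E.

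The documents give no rate at which a weight effect would fade. Assume f(t) = 2^(−t/h), with h the half-life of the weight effect:

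| h (days) | f(14), orvepitant column | f(63), placebo column | Difference |
|---|---|---|---|
| no fading | 1.00 | 1.00 | 0 |
| 60 | 0.85 | 0.48 | 0.37 E |
| 28 | 0.71 | 0.21 | 0.50 E |
| 14 | 0.50 | 0.04 | 0.46 E |
| 7 | 0.25 | 0.00 | 0.25 E |
| 3 | 0.04 | 0.00 | 0.04 E |

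The maximum is where 14·f(14) = 63·f(63), that is 2^(−49/h) = 14/63. This gives h ≈ 23 days and a difference of about 0.51 E.

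As an illustration, take an assumed true loss of 2 kg. With no fading, both columns show a 2 kg loss and the difference is 0. With h = 28 days, the columns show losses of 1.41 and 0.42 kg, a difference of 0.99 kg.

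**4. Drug level at Visit 8.** With the half-life of about 33 hours (Protocol 8.6.1), 14 days is 14 × 24/33 = 10.2 half-lives, or 8.0 to 12.4 over the ±3-day window. About 0.1% of the end-of-dosing level remains at the nominal day. An effect that follows plasma level closely would therefore have largely gone in both sequences before the only post-baseline weighing.

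**5. With weight at Visits 4, 5 and 7.** Visit 2 to 4 and Visit 5 to 7 would each cover one 28-day period on one treatment. Carry-over aside, the within-subject contrast estimates E.

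**The case against.** **The SAP may not call for a weight table.** SAP 8.3 omits weight, and Protocol 11.6 gives the SAP precedence. Protocol 10.2.8 itself describes the vital signs and then adds weight separately. This stands in part: a by-treatment weight summary follows only from the general sentence in SAP 8 and from Protocol 8.3 read with 11.9. But SAP 3.4 keeps weight as an endpoint and SAP 14.1 declares no change from the protocol analyses. The endpoint is therefore either analysed in a form that cannot be interpreted or dropped without saying so.

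**Nothing assigns the change to Period B.** A reader might infer that the Visit 2 to Visit 8 change is booked to the Period B treatment. The documents do not support that as fact. The fallback concerns a missing baseline and does not say whether this covers one never scheduled. For efficacy, the same section treats a baseline that is not available as a separate case. The explicit rules carrying Period B through to follow-up are for adverse events (SAP 8.1) and concomitant medications (SAP 6.4).

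**A signal would not vanish.** A reader might also infer that the table would show no effect whatever the truth. That is wrong. A lasting effect would appear as a change from baseline in both columns, and a fading one would leave a partial difference. Cohorts are randomised and shown separately, so the whole-study change also gives a fair comparison of 30 mg with 10 mg. What is lost is the comparison with placebo.

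**Some subjects are exempt.** Those who withdraw during Period A have the Visit 8 procedures then (Protocol 7.4), so their change reflects one treatment.

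**Little depends on it.** Safety is not formally tested. The adverse events of special interest are respiratory decline and suicidality, and no weight concern is flagged. Clinically significant vital-sign changes are also recorded as adverse events. This stands, and it limits the importance of the point. However, a weight change first found at Visit 8 cannot be dated to either period.

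**Conclusion.** The point holds, as a minor matter of descriptive safety reporting. With weight taken only at Visits 2 and 8, a completer's change covers 91 days and both treatments. It can show that weight changed over the study but not whether orvepitant changed it. This rests on the visit schedule alone, which the synopsis, Protocol 10.2.8 and Table 2 give consistently.

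The size depends on two assumptions outside the documents: that the change is labelled by Period B treatment, and that the effect fades exponentially. Under both, orvepitant-then-placebo subjects would count as placebo. The between-treatment difference would then lie between 0 (persistent effect) and about half of the true effect. The stronger reading, that an effect on weight would be hidden in every case, is not supported.

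Separately, SAP 3.4 and SAP 8.3 disagree on whether weight is analysed, and that needs resolving whichever course is taken.

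**What to change.** **Preferred.** Add weight to the vital signs already taken at Visits 4, 5 and 7 (Protocol 10.2.8, synopsis and the Table 2 footnote), and name it in SAP 8.3. Each treatment then has its own baseline and Week 4 value. The cost is three weighings at existing visits. These may be home visits, so a scale has to be brought; Visit 8, where weight is already required, may also be a home visit. Subjects already past these visits cannot supply the values.

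**Otherwise, wording only.** State in SAP 8.3 that weight is reported as a whole-study change from Visit 2 to Visit 8, by cohort and not by treatment, and that the Visit 2 fallback does not apply to it. List separately the subjects who withdraw during Period A. Bring the synopsis, Protocol 8.3 and SAP 3.4 into line. This needs no new data, but it gives up any comparison of weight between orvepitant and placebo.
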